4. ANALYSIS POPULATIONS

Population	Definition / Criteria	Analyses Evaluated
Screened	
 • All participants who were screened for eligibility 	
 • Study Population
Enrolled	
 • All participants who passed screening and entered the study (i.e. were administered study treatment). 	
 • Study Population
Safety	
 • All participants who received at least one dose of study treatment. 	
 • Study Population, Safety, Efficacy, Virology, PK, Other Assessments

Refer to Appendix 13: List of Data Displays which details the population used for each display.

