8. SAFETY ANALYSES

The safety analyses will be based on the Safety population, unless otherwise specified.

For the Month 12 and EOS analyses, safety displays will summarize data across the combined Intervention + Extension Phases, unless otherwise specified in the display title presented in Appendix 13: List of Data Displays.

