8.1.1. Injection Site Reaction Adverse Events

Injection Site Reaction (ISR) adverse events of interest are those from study drug injections.

For the summary of Injection Site Reaction Adverse Events by Visit and Maximum Severity (Overall and by Common ISRs), ISRs will be assigned based on onset date to the most recent planned IM injection visit prior or equal to the AE onset date.

Maximum grade at each visit will be derived as the maximum grade among ISRs assigned to the particular visit, with consideration for whether the summary applies to a particular preferred term (vs. across preferred terms), or drug-related associated to CAB and/or RPV.

Drug-related ISRs (based on investigator discretion) will be attributed to the causal agent (CAB vs. RPV) when this can be determined specifically based on the side of injection administration and the side of the reported ISR (as collected in the eCRF). If we are unable to determine the causal agent in those cases where both drugs are given on one side and the ISR is reported non-specifically, then the attribution to a specific causal agent will remain unknown.

Common study drug ISR adverse events are defined by MedDRA preferred terms including injection site pain, injection site induration, injection site nodules and preferred terms of any other ISR reported by $\geq 5\%$ of participants overall.

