13.4.3. Oral Lead-in Period

Certain displays will be produced for data collected or events occurring during the oral-lead-in period as defined in Table 11 and Table 12.

Table 11 Oral Lead-in Period for AEs

Study Period	Date Range
Oral Lead-in	
For participants receiving at least one Injection: Intervention Treatment Start Date \leq Date [a] $<$ Date of First IM Injection
 
For participants withdrawing prior to first Injection: Date \geq Intervention Treatment Start Date
 
Note that the oral lead-in period is only applicable to the participants who received at least one dose of study treatment during the oral lead-in period in the study. Oral lead-in period is within the intervention phase.

[a] AEs with completely missing start date which have been assigned to the Intervention Phase based on Table 6 will not be assigned to the Oral Lead-in Period.

NOTES:

- Date = AE Start date

Table 12 Oral Lead-in Period for Laboratory Data

Period	Date Range
Oral Lead-in	
For participants receiving at least one Injection: Intervention Treatment Start Date $<$ Date \leq Date of First IM Injection
 
For participants withdrawing prior to first Injection: Date $>$ Intervention Treatment Start Date
 
Note that the oral lead-in period is only applicable to the participants who received at least one dose of study treatment during the oral lead-in period in the study. Oral lead-in period is within the intervention phase.

NOTES:

- Date = Date of assessment

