
 The Study Day of an event (e.g., lab assessment, vital sign, ECG, start date of AE or HIV associated condition) will be derived as the number of days between the date of the event and the Intervention Phase treatment start date as follows: 
 If date of event \geq start date of study treatment, then 
 Study Day = Date of Event - Intervention Phase Treatment Start Date + 1 If date of event $<$ start date of study treatment, then 
 Study Day = Date of Event - Intervention Phase Treatment Start Date Note that the start date of intervention phase study treatment is on Study Day 1 and the day before this is Study Day -1; i.e., there is no Study Day 0.
Long Term Follow-up Study Day

 The Long-Term Follow Up (LTFU) Study Day of an event (e.g., lab assessment, start date of AE or HIV associated condition) will be derived as the number of days between the date of the event and the end of IP treatment [i.e. max(Last IM Injection Date, Last Oral Bridging End Date)] as follows: 
 If the date of event falls in Long-term Follow up phase, then 
 LTFU Study Day = Date of event - End date of IP + 1
Study Treatment

 Refers to CAB+RPV oral lead-in, CAB + RPV oral bridging, SOC oral bridging, CAB LA + RPV LA

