3.13.	Safety	AE3	Summary Drug-Related Adverse Events by Overall Frequency	ICH E3	M12, EOS
3.14.	Safety	AE5B	Summary of Drug-Related Adverse Events by System Organ Class and Maximum Grade	ICH E3	HL, M12, EOS
3.15.	Safety	AE5B	Summary of Drug-Related Adverse Events by System Organ Class and Maximum Grade — Excluding Study Drug Injection Site Reactions		M12, EOS
3.16.	Safety	AE15	Summary of Common (>=5%) Non-serious Adverse Events by System Organ Class and Preferred Term (Number of Subjects and Occurrences)	FDAAA, EudraCT	M12, EOS
3.17.	Safety	AE3	Summary of Common (>=1%) Drug-Related Grade 2-5 Adverse Events by Overall Frequency	ICH E3	M12, EOS
3.18.	Safety	AE3	Summary of Non-Serious Drug-Related Adverse Events by Overall Frequency	Plain Language Summary requirements.	M12, EOS

Safety: Tables					
No.	Population	GSK Standard/ Example Shell	Title	Programming Notes	Deliverable
Serious and Other Significant Adverse Events					
3.19.	Safety	AE5B	Summary of Serious Adverse Events by System Organ Class and Maximum Grade	ICH E3	HL, M12, EOS
3.20.	Safety	AE16	Summary of Serious Adverse Events by System Organ Class and Preferred Term (Number of Subjects and Occurrences)	FDAAA, EudraCT	M12, EOS
3.21.	Safety	AE1	Summary of Adverse Events Leading to Permanent Discontinuation of Study Treatment or Withdrawal from Study by System Organ Class and Preferred Term	GSK Statistical Display Standard	HL, M12, EOS
3.22.	Safety	AE20	Summary of Serious Fatal and Non-Fatal Drug-Related Adverse Events by Overall Frequency	Plain Language Summary requirements.	M12, EOS
Injection Site Reaction Adverse Events					
3.23.	Safety	201584/primary_7/T3.40	Summary of Study Drug Injection Site Reaction Adverse Events (Event-level Summary)		HL, M12, EOS
3.24.	Safety	201584/primary_7/T3.43	Summary of Subject-level Characteristics of Study Drug Injection Site Reaction Adverse Events – Overall and Common		HL, M12, EOS
3.25.	Safety	201584/primary_7/T3.46	Summary of Study Drug Injection Site Reaction Adverse Events by Visit and Maximum Severity – Overall and Common		HL, M12, EOS

Safety: Tables					
No.	Population	GSK Standard/ Example Shell	Title	Programming Notes	Deliverable
Laboratory: Chemistry					
3.26.	Safety	LB1	Summary of Chemistry Values	Includes pre-specified parameters repeated in conventional units. Includes baseline values	M12, EOS
3.27.	Safety	LB1	Summary of Chemistry Changes from Baseline	ICH E3	M12, EOS

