13.13.8. Safety Figures

Safety: Figures					
No.	Population	GSK Standard / Example Shell	Title	Programming Notes	Deliverable
Adverse Events					
3.1.	Safety	201584/primary_07/F3.14	Plot of Incidence of Intervention Phase Study Drug Injection Site Reaction Adverse Events by Visit (Overall and Common) – CAB and/or RPV	For EOS, remove “Intervention Phase” from the title and include all ISRs from Intervention or Extension phase.	M12, EOS
3.2.	Safety	201584/primary_07/F3.17	Plot of Incidence of Grade 3-5 Intervention Phase Study Drug Injection Site Reaction Adverse Events by Visit (Overall and Common) - CAB and/or RPV	For EOS, remove “Intervention Phase” from the title and include all Grade 3-5 ISRs from Intervention or Extension phase.	M12, EOS
Laboratory					
3.3.	Safety	LIVER14	Scatter Plot of Maximum vs. Baseline for ALT	GSK Statistical Display Standard	M12, EOS
3.4.	Safety	LIVER9	Scatter Plot of Maximum Total Bilirubin vs Maximum ALT – eDISH Plot	GSK Statistical Display Standard	M12, EOS

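### Subject-level injection site reaction (ISR) percentages are assigned to a Safety population that includes never-injected participants, and the by-visit ISR displays state no at-risk denominator

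*SAP*

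**What the plan says.** Section 4 defines Safety as "All participants who received at least one dose of study treatment". Section 13.6.1 says what study treatment covers: "Refers to CAB+RPV oral lead-in, CAB + RPV oral bridging, SOC oral bridging, CAB LA + RPV LA". One day of oral lead-in is therefore enough to enter the population.

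The plan provides for people who never reach an injection. Assessment-window Tables 1 and 2 have rows for them, and the oral lead-in definitions in Section 13.4.3 (Tables 11 and 12) carry a rule headed "For participants withdrawing prior to first Injection".

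Section 8 sets the default: "The safety analyses will be based on the Safety population, unless otherwise specified". Section 4 refers to Appendix 13 for the population of each display. There, Tables 3.23 to 3.25 (Table 3.24 being the "Summary of Subject-level Characteristics of Study Drug Injection Site Reaction Adverse Events") and Figures 3.1 and 3.2, including the "Plot of Incidence of Intervention Phase Study Drug Injection Site Reaction Adverse Events by Visit", all show Safety. The tables' programming notes are blank. The figures' notes deal only with the title and the phases covered at end of study.

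Section 8.1.1 assigns each ISR to the latest planned injection visit on or before onset. It treats pain, induration and nodules as common whatever their frequency, and adds "preferred terms of any other ISR reported by" at least 5% of participants overall. It names no at-risk denominator, either overall or by visit.

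**The concern.** A participant who was never injected is not at risk of a reaction at an injection site. Counting that person among the participants, but never among the cases, can only lower the percentage. ISRs across the study are a listed secondary endpoint (Section 2.2), and Tables 3.23 to 3.25 are Month 12 headline deliverables, so these figures are likely to be quoted.

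For the by-visit displays the question is wider than oral-only participants. Section 13.6.2 foresees missed injections, with and without oral bridging, and discontinuation partway through. If the denominator stayed at the Safety N throughout, the number at risk would fall while the denominator did not. Part of any apparent decline in ISRs over the year could then be an artefact.

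**Working it through.** The SAP gives no ISR incidence and no count of never-injected participants, so there is no figure of its own to reproduce. The inputs are N = 115 (Section 2.3) and k, the number never injected, which is an assumption and is varied.

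**Subject-level incidence (Table 3.24).** If p is the incidence among the injected, then on the Safety denominator:

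shown incidence = p × (115 − k) / 115

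The relative loss is k/115. With p = 80% (illustrative):

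| k | Injected | Shown on Safety N | Loss (points) |
|---|---|---|---|
| 0 | 115 | 80.0% | 0 |
| 1 | 114 | 79.3% | 0.7 |
| 3 | 112 | 77.9% | 2.1 |
| 5 | 110 | 76.5% | 3.5 |
| 10 | 105 | 73.0% | 7.0 |

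**By-visit incidence (Table 3.25, Figures 3.1 and 3.2), if the Safety N is used at every visit.** With m participants injected at a visit and a constant 30% risk among them (both assumed), the shown value is 0.30 × m / 115:

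- m = 110: 33/115 = 28.7%
- m = 100: 30/115 = 26.1%
- m = 90: 27/115 = 23.5%

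The risk has not changed, but the plotted line falls.

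**The 5% rule for common ISRs.** The smallest qualifying count is 5% of the denominator, rounded up:

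- Denominator 115: 5.75, so 6 participants
- Denominator 112, 110 or 105 (k = 3, 5, 10): 5.60, 5.50 or 5.25, so 6 in each case
- Denominator 101 (k = 14): 5.05, so 6
- Denominator 100 (k = 15): 5.00, so 5

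A term changes class only if at least 15 of 115 were never injected. At the stated maximum of 135 the threshold is 7 (6.75 rounded up), and it falls to 6 at the same k = 15 (5% of 120 is 6.00).

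**Event-level table.** Table 3.23 is the "Summary of Study Drug Injection Site Reaction Adverse Events (Event-level Summary"). Counts of events and percentages of events do not use the number of participants, so k does not enter.

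**The case against.** The best counter-argument is that the Population column does not settle a display's denominator. The SAP puts Safety on displays that are plainly restricted: Tables 3.40 to 3.42 (participants with COVID-19 events), Table 4.1 (confirmed virologic failure), Listing 45 (oral bridging) and the adherence tables, where Section 13.6.2 counts only expected injection visits. The ISR displays follow shells from study 201584, which are not shown and may already use the number injected. The study is also descriptive, has no comparator, and reports exposure, so a reader could work out who was injected.

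Part of this stands. For Table 3.25 and the figures, dilution is possible but not established; the defect there is an unstated denominator. It does not clear Table 3.24. In the other displays the restriction is written in the title or in a derivation section, whereas for the subject-level ISR table neither Appendix 13 nor Section 8.1.1 contains one. A shell from another study that cannot be seen does not override the population the SAP states.

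A reader might go further and infer that the list of common ISRs would change, or that every ISR display is biased. The documents support neither. The threshold count does not move below 15 never injected, three terms bypass it altogether, and Table 3.23 is event-level.

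**Conclusion.** The point holds for Table 3.24 as the SAP is written. Its stated population includes people not at risk, and the resulting bias has one direction. For Table 3.25 and Figures 3.1 and 3.2, the finding is that no by-visit denominator is given, with dilution following only if the Safety N is carried across visits.

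The size rests on k, which the SAP does not supply. At an assumed 80% incidence the loss is 2.1 points for k = 3 and 3.5 points for k = 5, and it is nil if everyone was injected. The rules for pre-injection withdrawal show that such participants were foreseen. It would be wrong to read them as showing that there were any, or many. This is probably a modest effect, worth correcting because a named endpoint is involved and the correction is cheap.

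**What to change.** Add to Section 8.1.1, and repeat in the programming notes for Tables 3.24 and 3.25 and Figures 3.1 and 3.2:

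- Subject-level ISR percentages use Safety participants with at least one CAB LA and/or RPV LA injection. For consistency, the 5% rule uses the same denominator.
- By-visit ISR percentages use participants injected at that visit. Make clear that an ISR is assigned to a visit at which an injection was actually given, so that the numerator lies within the denominator.

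Table 3.23 needs no change. A flag or a footnote is enough, and no new population in Section 4 is required. The SAP already restricts other rules to participants with at least one injection (Table 5 and the long-term follow-up rows of Tables 6 and 7), so the flag comes from dates already collected. The cost is a few lines of text and programming, and ISR percentages that are slightly less favourable to the regimen. Other safety displays stay on Safety as planned.

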13.13.8. Safety Figures

Safety: Figures					
No.	Population	GSK Standard / Example Shell	Title	Programming Notes	Deliverable
Adverse Events					
3.1.	Safety	201584/primary_07/F3.14	Plot of Incidence of Intervention Phase Study Drug Injection Site Reaction Adverse Events by Visit (Overall and Common) – CAB and/or RPV	For EOS, remove “Intervention Phase” from the title and include all ISRs from Intervention or Extension phase.	M12, EOS
3.2.	Safety	201584/primary_07/F3.17	Plot of Incidence of Grade 3-5 Intervention Phase Study Drug Injection Site Reaction Adverse Events by Visit (Overall and Common) - CAB and/or RPV	For EOS, remove “Intervention Phase” from the title and include all Grade 3-5 ISRs from Intervention or Extension phase.	M12, EOS
Laboratory					
3.3.	Safety	LIVER14	Scatter Plot of Maximum vs. Baseline for ALT	GSK Statistical Display Standard	M12, EOS
3.4.	Safety	LIVER9	Scatter Plot of Maximum Total Bilirubin vs Maximum ALT – eDISH Plot	GSK Statistical Display Standard	M12, EOS

13.13.9. Virology Tables

No.	Population	GSK Standard / Example Shell	Title	Programming Notes	Deliverable
4.1.	Safety	201584/primary_17/T7.2	Viral load, Genotypic and Phenotypic data for Subjects Who Met Confirmed Virologic Failure Criteria		HL, M12, EOS
4.2.	Safety	201584/primary_17/T7.4	Viral Load, Genotypic and Phenotypic Data for Non-CVF Subjects	Only include subjects with available genotypic or phenotypic data.	M12, EOS

13.13.10. Other Tables

Study Visit Length					
No.	Population	GSK Standard / Example Shell	Title	Programming Notes	Deliverable
5.1.	Safety	OTR_T1	Summary of Study Visit Length (minutes) by Visit and Site Type (Intervention Phase)		HL, M12
5.2.	Safety	OTR_T1	Summary of Study Visit Length (minutes) by Visit and Site (Intervention Phase)		HL, M12

13.13.11. ICH Listings

ICH: Listings					
No.	Population	GSK Standard / Example Shell	Title	Programming Notes	Deliverable
Subject Disposition					
1.	Enrolled	ES2	Listing of Reasons for Study Withdrawal	ICH E3 Add column for Phase	M12, EOS
2.	Enrolled	SD2	Listing of Reasons for Study Treatment Discontinuation	ICH E3 Add column for Phase	HL, M12, EOS
Protocol Deviations					
3.	Enrolled	DV2	Listing of Important Protocol Deviations	ICH E3 Add column for Phase Add a column on the right for "COVID-19 Related". The possible values in this column are Y and N, where Y indicates the deviation is COVID-19 related and N indicates the deviation is non-COVID-19 related.	M12, EOS
4.	Enrolled	DV2	Listing of Protocol Deviations Related to COVID-19	FDA Request Add column for Phase	HL, M12, EOS
5.	Safety	IE3	Listing of Subjects with Inclusion/Exclusion Criteria Deviations	ICH E3	M12, EOS
Populations Analysed					
6.	Enrolled	SP3	Listing of Subjects Excluded from Safety Population	ICH E3	M12

ICH: Listings					
No.	Population	GSK Standard / Example Shell	Title	Programming Notes	Deliverable
Demographic and Baseline Characteristics					
7.	Safety	DM2	Listing of Demographic Characteristics	ICH E3	M12, EOS
8.	Safety	DM9	Listing of Race	ICH E3	M12, EOS
Efficacy					
9.	Safety	SNAPSHOT11	Listing of Qualitative and Quantitative Plasma HIV-1 RNA Data		HL, M12, EOS
10.	Safety	SNAPSHOT12	Listing of Study Outcome (50 copies/mL cutoff) at Month 12 – Snapshot Analysis	Include both original and LOCF imputed outcomes	HL, M12
11.	Safety	VF4	Listing of Plasma HIV-1 RNA and CD4+ Cell Count for subjects with Confirmed Virologic Failure		M12
Exposure and Treatment Compliance					
12.	Safety	207966/primary_15/L12	Listing of Exposure Data	ICH E3 Remove Phase Day	M12, EOS
Adverse Events					
13.	Safety	AE8	Listing of All Adverse Events	ICH E3 Add Phase/Period, Side/Drug, see gsk1265744/mid207966/primary_15/L19	HL, M12, EOS
14.	Safety	AE8	Listing of Grade 3-5 Adverse Events	Add Phase/Period, Side/Drug, see gsk1265744/mid207966/primary_15/L19	M12
15.	Safety	AE7	Listing of Subject Numbers for Individual Adverse Events	ICH E3	M12, EOS

ICH: Listings					
No.	Population	GSK Standard / Example Shell	Title	Programming Notes	Deliverable
16.	Safety	PSRAE1	Listing of Possible Suicidality-Related Adverse Event Data: Event and Description (Section 1-Section 2)	Add Phase	M12
17.	Safety	PSRAE3	Listing of Possible Suicidality-Related Adverse Event Data: Possible Cause(s) (Section 3)	Add Phase	M12
18.	Safety	PSRAE4	Listing of Possible Suicidality-Related Adverse Event Data (Section 4)	Add Phase	M12
19.	Safety	PSRAE5	Listing of Possible Suicidality-Related Adverse Event Data (Section 5-Section 8)	Add Phase	M12
20.	Safety	201584/primary_07/L22	Listing of Changes in Intensity/Grades of Study Drug Injection Site Adverse Events	Remove phase treatment	M12, EOS
21.	Safety	AE8	Listing of COVID-19 Adverse Events	Add Phase/Period, Side/Drug, see gsk1265744/mid207966/primary_15/L19	HL, M12, EOS
22.	Safety	PAN12	Listing of COVID-19 Assessments and Symptom Assessments		M12, EOS
23.	Safety	PAN5	Country Level Listing of Start Dates of COVID-19 Pandemic Measures	For EOS: change the title to be "Country Level Listing of Dates of Waves of COVID-19 Pandemic Measures" and use the PAN5A shell.	M12, EOS
Serious and Other Significant Adverse Events					
24.	Safety	AE8	Listing of Fatal Serious Adverse Events	ICH E3 Add Phase/Period, Side/Drug	M12, EOS

ICH: Listings					
No.	Population	GSK Standard / Example Shell	Title	Programming Notes	Deliverable
25.	Safety	AE8	Listing of Non-Fatal Serious Adverse Events	ICH E3 Add Phase/Period, Side/Drug	M12, EOS
26.	Safety	AE14	Listing of Reasons for Considering as a Serious Adverse Event	ICH E3	M12, EOS
27.	Safety	AE8	Listing of Adverse Events Leading to Withdrawal from Study / Permanent Discontinuation of Study Treatment	ICH E3 Add Phase/Period, Side/Drug	M12, EOS
28.	Safety	AE8	Listing of All Adverse Events with Completely Missing Onset Date, Missing Relationship to Study Treatment, Severity and/or Grade	ICH E3 Add Phase/Period, Side/Drug, see gsk1265744/mid207966/primary_15/L19	M12
Laboratory					
29.	Safety	UR2	Listing of Urinalysis Data for Subjects with Any Value of Potential Clinical Importance	ICH E3 Include Grade Note: Potential Clinical Importance is defined as: 1. Increase in Protein (dipstick) or Occult Blood (dipstick) post-baseline relative to baseline 2. Increase in any DAIDS graded values for Protein, Occult Blood or Glucose relative to baseline 3. If microscopy is performed.	M12, EOS

13.13.12. Non-ICH Listings

Non-ICH: Listings					
No.	Population	GSK Standard GSK Statistical Display Standard / Example Shell	Title	Programming Notes	Deliverable
Subject Disposition					
30.	Screened	ES7	Listing of Reasons for Screen Failure	Journal Guidelines	M12, EOS
31.	Screened	ES9	Listing of Subjects Who Were Rescreened		M12, EOS
32.	Safety	TA1	Listing of Planned and Actual Treatments	GSK Statistical Display Standard	M12
Prior and Concomitant Medications					
33.	Safety	207966/primary_15/Listing 36	Listing of Prior ART Medications	Remove the column 'Phase during Which Concomitant'	M12, EOS*
34.	Safety	207966/primary_15/Listing 37	Listing of Concomitant ART Medications	In case the same medication is concomitant during both intervention and extension phases, list each of them in two separate rows. Add a column "SOC Oral Bridging?" which has values of "Yes" and "No".	HL, M12, EOS
35.	Safety	207966/primary_15/Listing 38	Listing of ART Medications Received during Long-term Follow-up Phase	Remove the column 'Phase during Which Concomitant' and "Start Date of the Long-term Follow-up ART/Study Day".	M12, EOS

Non-ICH: Listings					
No.	Population	GSK Standard GSK Statistical Display Standard / Example Shell	Title	Programming Notes	Deliverable
51.	Safety	POP_L2	Listing of COVID-19 Vaccine		EOS
Medical History					
36.	Safety	201584/primary_01/L43	Listing of Medical History of Seizure		M12, EOS*
Transition to CAB + RPV LA Marketed Product Status					
52.	Safety	POP_L1	Listing of Transition to CAB + RPV LA Marketed Product Status		EOS
Efficacy					
37.	Safety	CDC4	Listing of CDC Classification of HIV-1 Infection at Baseline		M12, EOS*
38.	Safety	CDC5	Listing of CDC Stage 3 HIV-1 Associated Conditions	Add Phase	EOS
Hepatobiliary (Liver)					
39.	Safety	LIVER5	Listing of Liver Monitoring/Stopping Event Reporting	GSK Statistical Display Standard	M12, EOS
40.	Safety	LIVER15	Liver Stopping Event Profile	GSK Statistical Display Standard	M12
41.	Safety	LIVER13	Listing of Subjects Meeting Hepatobiliary Laboratory Criteria Post-Baseline	GSK Statistical Display Standard	HL, M12, EOS
42.	Safety	LB12	Listing of ALT, AST, Bilirubin (including Total and Direct Bilirubin), INR, and ALP for Subjects Meeting Hepatobiliary Lab Abnormality Criteria	Add Phase	M12, EOS

Non-ICH: Listings					
No.	Population	GSK Standard GSK Statistical Display Standard / Example Shell	Title	Programming Notes	Deliverable
ECG					
43.	Safety	EG3	Listing of All ECG Values for Subjects with Any Value of Potential Clinical Importance	GSK Statistical Display Standard By default, the definition of PCI is defined based on QTc value (e.g., QTcF Interval, Aggregate) where a subject has a QTc value >450 or a QTc increase of >30msec.	M12, EOS
44.	Safety	EG5	Listing of All ECG Findings for Subjects with an Abnormal ECG Finding	GSK Statistical Display Standard	M12, EOS
Other					
45.	Safety	207966/primary_15/L60	Listing of Exposure Data for Subjects Receiving Oral Bridging	Add column to identify COVID relatedness.	HL, M12, EOS
46.	Safety	207966/primary_15/L61	Listing of Dosing Errors and IP Device Malfunctions	Add Phase	M12, EOS
47.	Safety	PREG1	Listing of Subjects or Partners Who Became Pregnant During the Study	GSK Statistical Display Standard	M12, EOS
48.	Safety	201584/primary_17/L54	Listing of Replication Capacity in IN and PR/RT Region	Add Phase	M12
PK Endpoints					
49.	Safety	PK07	Listing of Plasma CAB Pharmacokinetic Concentration-Time Data	Add column 'Reason for Collection' on the right.	M12, EOS

Non-ICH: Listings					
No.	Population	GSK Standard GSK Statistical Display Standard / Example Shell	Title	Programming Notes	Deliverable
50.	Safety	PK07	Listing of Plasma RPV Pharmacokinetic Concentration-Time Data	Add column 'Reason for Collection" on the right.	M12, EOS

